The influence of daily grapes' intake on sarcopenia in postmenopausal women

1) Protocol Title

The influence of daily grapes' intake on sarcopenia in postmenopausal women

Protocol Version Date:

This is a new IRB submission

2) Objectives

The objective of this project is to evaluate whether the daily consumption of a freeze-dried table grape powder, rich in phenolic compounds, mitigates sarcopenia in postmenopausal women. To achieve this objective, we will pursue the following aims:

1. To determine the efficacy of a freeze-dried table grape powder, rich in phenolic compounds, to mitigate sarcopenia parameters in postmenopausal women.
1. To evaluate the effect of a freeze-dried table grape powder on key metabolic regulators of sarcopenia in postmenopausal women, specially irisin.

We hypothesize that daily dietary supplementation with a grape powder improves health span, mitigates sarcopenia parameters and increases irisin plasma levels in postmenopausal women.

[figure not shown]
The successful completion of this pilot human study will provide evidence on the benefit of the daily addition of table grape to the diet of healthy older women to improve sarcopenia by regulating some key metabolic regulators. This will provide strong preliminary results to apply for competitive grant (USDA) in order to expand these findings using a bigger sample size, multiple doses and various time-periods.

3) Background

As stated above, sarcopenia is defined as a loss of muscle strength and mass in older individuals. However, until recently, there has been no widely accepted definition of

sarcopenia that was suitable for use in research and clinical. Sarcopenia leads to fragility and disability, worsens the prognosis of many diseases, and significantly enhances morbidity and mortality. Furthermore, a higher risk of death from all causes compared with non-sarcopenic subjects was found in > 60 years old and mainly in > 80 years old (13, 14). With the increasing life expectancy and rapid growth of the aged population, sarcopenia is becoming an emerging public health issue with huge socioeconomic burden.

In recent years, various international consensuses have brought these fundamental concepts to the clinical practice. The European Working Group on Sarcopenia in Older People (EWGSOP) developed a practical clinical definition and consensus diagnostic criteria for age-related sarcopenia, recommending the use of the presence of both low muscle mass and low muscle function (strength or performance) for diagnosis. Recently, a new consensus (EWGSOP2) recommended low muscle strength as the primary parameter to assess sarcopenia and new

[figure not shown]
cut-off points to increase harmonization of sarcopenia studies (15).

Given the above, there is an ongoing intensive search for novel therapies, including dietary ones that can attenuate the loss of muscle mass and strength in the elderly (10, 16). Interestingly, a growing body of research indicate that nutritional factors can preserve muscle function from age-related decline. In particular, phenolic compounds, widely distributed in fruits including grapes, have shown beneficial effects in muscle health (17, 18). Phenolic compounds have garnered attention because they ability to alleviate disease pathologies through anti-inflammatory, anti-carcinogenic and antioxidant

properties. However, the exact influence of grapes and grapes phenolic compounds mitigating sarcopenia in humans remains unexplored.

A novel and understudied mechanism by which skeletal muscle might mediate their protective effect against sarcopenia is by secreting myokines. Irisin is a myokine regulated by peroxisome proliferator-activated receptor gamma co-activator-1 α (PGC-1 α) and released into the bloodstream after cleavage of the Fibronectin type III domain-containing protein 5 (FNDC5) (**Fig 1.**). Recent studies have indicated that circulating irisin can promote skeletal muscle growth (12, 19, 20). Lower irisin concentrations have been observed in sarcopenia patients (21) and dialyzed patients with cardiovascular disease (22). Furthermore, lower irisin plasma levels are associated with sarcopenia in postmenopausal women (10).

In a recent study, we have shown that phenolic compounds present in a grape pomace extract (GPE), prevent irisin downregulation in rats fed a high-fat diet and in L6 myotube cells. In particular, we documented that consumption of the GPE activates the FNDC5/irisin pathway, with a significant increase of PGC-1 α and FNDC5 protein

levels compared to control and high fat diet groups (**Figure 2A-B**). Furthermore, supplementation with GPE led to the increase in irisin plasma level (**Figure 2C**)(11).

In order to understand the underlying mechanism involved in the GPE-related irisin increased levels, we next evaluated the effects of epicatechin, one of the main flavonoids present in GPE, in L6 myotubes challenged with palmitate, to mimic a condition of fatty acids oversupply. Protein levels of PGC- 1 α and FNDC5 were significantly higher in the EC and palmitate-treated cells, compared with palmitate-treated cells (**Figure 3A-B**). The same tendency was observed by immunocytochemical analysis of PGC-1 α , while no differences were observed in FNDC5 fluorescence intensity among treatments (**Figure 3D-E**). In addition, EC induced a 2-fold increase in irisin levels secreted to the medium compared with cells treated with only palmitate (**Figure 3C**). These data strongly indicate that phenolic compounds enhance irisin levels in vitro and in vivo.

These intriguing data allow us to hypothesize that phenolic compounds present in grapes might have a positive effect in human health, specially preventing sarcopenia in elderly humans, in part, by increasing irisin levels.

4) Enrollment Numbers

We chose the “changes in plasma irisin levels” as our primary outcome to determine the power calculations for sample size. Based on our preliminary data (11), 5 individuals per group are required to reach 80% power to detect differences in irisin levels between the groups, at a $\alpha=0.05$, using a two-sided paired T-test. We propose to enroll 7 individuals per group, instead of 5, in the event of a patient drop out of the study (for any unforeseen circumstances). In total we will have 14 subjects.

5) Inclusion and Exclusion Criteria

Inclusion Criteria: postmenopausal women aged 60 years or older with a hand-grip strength media value of 16 kg or lower, normal body mass index (BMI) with values between 18.4 and 24.9 kg/m², blood pressure below 130/80 mmHg, and plasma glucose and cholesterol concentrations below 100 and 200 mg/dl.

Exclusion Criteria: history of specific muscle diseases, peripheral vascular disease, intermittent claudication, central and peripheral nervous system disorders, cachexia, active diagnosis of diabetes mellitus, myocardial infarction, stroke, liver disease, on dialysis or long-term steroid therapy, and/or actively receiving treatment for cancer or severe infection (excluding short-term antibiotic therapy), weight less than 140 pounds, anemia and blood donations in the past 30 days. In addition, participants should not be taking dietary supplements at the time of the study.

6) Recruitment Methods

We will recruit by: 1) posting flyers on campus bulletin boards; 2) listing the study on our departmental website that provides a list of all current departmental trials; 3) listing the study on campus list servers; 4) advertising in the local newspapers and 5) posting on social media. All recruitment material will use similar language and list a study office phone number, clinical coordinator email and the departmental website for clinical trials (**Attachment A**). Respondents will be contacted by phone and pre-screened. Information about the study will be provided during the phone interview (**Attachment B**). For subjects that are eligible and interested in enrolling in the study, an in-person screening visit 1 appointment will be scheduled with the investigator or designee and the informed consent form emailed to them in advance. If the participants meet all the inclusion criteria, in the same visit the investigator or designee will review the informed consent form with the subjects, explain the study to the subjects and answer any questions prior signing the consent. Only once the informed consent form is signed, a diet history questionnaire (**Attachment C**) will be completed by the subjects.

7) Compensation to the Subjects

Subjects will be compensated at a rate roughly proportional to the inconvenience

incurred according to the following schedule:

- Visit 0 (screening): \$50 for inconvenience
- Visit 1: \$75 for inconvenience
- Visit 2: \$75 for inconvenience
- Visit 3: \$75 for inconvenience + \$50 for study completion

Subjects will be paid at the completion of their involvement in the study. The total compensation that a participant might earn is \$325 for completion of all visits. Subjects that withdraw from the study early will be compensated based on the visit(s) they completed.

8) Screening procedures to determine eligibility:

After being pre-screened for eligibility by a phone interview, eligible potential participants will come to the Ragle Facility in a fasting (12 h) state for the in-person screening **visit 0**. In this visit the participants will sign an informed consent form. The subject will read the information carefully and will be given the opportunity to seek more information if needed. The investigator or designee will obtain written (signed and dated by the subject) informed consent from each potential participant after adequate explanation of the aims, methods and potential hazards of the study. The investigator or designee will also explain to the potential participant that his/her participation is voluntary, and he/she is free to withdraw from the study at any time. The investigator or designee will sign and date the consent form to confirm that the consent process was completed correctly. The subject will also be provided with the option of taking the consent form home to review prior to making his/her decision. The subject will be provided with a copy of his/her signed and dated consent form. Once consent has been obtained, the pre-screening visit will proceed. After the subject has signed the informed consent, an identification number (ID) will be assigned and entered the screening and enrollment log. A diet history questionnaire (**Attachment C**) will be complete by the participant.

After this we will confirm if they meet the following inclusion criteria:

1- Hand-grip strength media value of 16 kg or lower: Handgrip strength will be evaluated by using a digital dynamometer (Grip Strength Dynamometer T.K.K.5401; Takei Co., Tokyo, Japan). Following are the steps of the procedure [a detailed procedure will be added (**Attachment D**)]:

- The participant will be asked to seat comfortably in a standard chair with legs, back support and fixed arms.
- The participant will be asked to rest their forearms on the arms of the chair with their wrist just over the end of the arm of the chair wrist in a neutral position, thumb facing upwards.
- The person in charge of the test will demonstrate how to use the handgrip dynamometer.
- The participant will be asked to start with the right hand.
- The person in charge of the test will encourage the participant to squeeze as long and as tightly as possible or until the needle stops rising. Once the needle stops rising the participant can be instructed to stop squeezing.
- The person in charge of the test will read grip strength in kilograms from the outside dial and record the result to the nearest 1 kg on the data entry form.
- The person in charge of the test will ask the participant to repeat measurement in the left hand.
- The participant will be asked to repeat two further measurements for each hand alternating sides to give three readings in total for each side.
- The best of the 3 grip strength measurements will be used in statistical analyses to encourage the subjects to get as high a score as possible.
- The person in charge will also record hand dominance, i.e. right, left or ambidextrous (people who can genuinely write with both hands).

For those participants that meet the previous inclusion criteria the following parameters will be explored:

1. Seated resting blood pressure.
2. Weight and height.

3. A finger stick blood sample (~1-2 drop equal to ~ 100ul) will be collected to confirm that subjects meet the inclusion criteria for fasting levels of blood glucose and cholesterol, plus a hematocrit to discard anemia.

Briefly, at Visit 0 (screening visit):

- Subjects will arrive fasted for at least 12 h prior to this visit (water ok).
- Informed consent will be obtained.
- ID number will be assigned.
- Hand grip strength test will be conduct.
- Seated resting blood pressure will be measured.
- Weight and height will be measured.
- A finger stick blood sample (~1-2 drop equal to ~ 100ul) to confirm that subjects meet the inclusion criteria (glucose, cholesterol and hematocrit).
- Diet history questionnaire (**Attachment C**) will be completed by the subjects to review medical history (including known positivity test for COVID-19), concomitant medications (including COVID-19 immunization dates), inclusion and exclusion criteria.
- This visit will take approximately 2 h to complete

9) Procedures Involved

Schedule of procedures

	Visit 0 Screening	Visit 1 Baseline	Visit 2 3-weeks visit	Visit 3 6-weeks final visit
Informed consent	X			
Inclusion / Exclusion criteria	X			
Review medical history	X			
Review concomitant medications	X		X	
Height, weight and blood pressure	X	X	X	X
Finger stick		X	X	X
Hand grip strength test	X	X	X	X
SPPB test		X	X	X

Blood draws for plasma determinations	X	X	X	X
Hematocrit	X	X	X	X
Study product randomization		X		
Study product intake			X	X
Dispense study product for home		X	X	
Return unused study product and empty packages			X	X
Dispense stool and urine collection kit		X	X	
Return stool and urine collection kit			X	X
Adverse events assessment			X	X

After confirmation of the inclusion/exclusion criteria enrolled subjects will be asked to travel to Ragle Human Nutrition Center at University of California Davis for 3 study visits: a baseline visit (**visit 1**), and a 3-week intervention visit (**visit 2**) and a final 6-week visit (**visit 3**)

Visit 1 (baseline visit):

On this visit, baseline measurement will be done. Fasted participants (12 h) will provide blood samples and complete two tests:

Blood samples: from each participant 20 ml of blood will be extracted. The following parameters will be measured in plasma, (the same parameters will be measure in the following visits 2 and 3):

Blood parameter	Volume of blood needed	Visit 1	Visit 2	Visit 3
Irisin	1200 ul	X	X	X
Glucose	1000 ul	X	X	X
Insulin	1200 ul	X	X	X
GLP-1/ 2, GIP	2000 ul	X	X	X
Adiponectin, leptin and ghrelin	3000 ul	X	X	X
Blood urea nitrogen, creatinine	1000 ul	X	X	X
Total cholesterol, triglyceride, high-density lipoprotein (HDL), low-density lipoprotein	2000 ul	X	X	X
Aspartate transaminase, Alanine transaminase	2000 ul	X	X	X
IL-6, IL-15	2000 ul	X	X	X
25-hydroxyvitamin D	1000 ul	X	X	X
Hematocrit	500 ul	X	X	X

Total volume of blood per visit	~ 20 ml	20 ml	20 ml	20 ml
---------------------------------	---------	-------	-------	-------

After taking the blood samples a snack will be provided to the participants in order to complete the following tests.

1. Hand-grip strength: previously described in the screening point
2. Short Physical Performance Battery (SPPB): the SPPB score will be based on three tests, as follows: balance test, gait speed test, and chair stand test (see **Attachment E**). Of note, these tests have been used as a predictive tool for possible disability and can aid in the monitoring of function in older people.

Following, the subjects will randomize into the study supplement: a) Placebo powder (46 g placebo powder in 180 ml of water); or b) freeze-dried table grape powder (46 g grape powder in 180 ml of water). The supplement will be supplied to the participants to complete the following 3 weeks supplementation until the next visit. The investigator or designee will explain the details regarding the preparation and consumption of the supplement [a dosing protocol will be uploaded too (**Attachment F**)].

Also a 24-hs food and physical activity questionnaire will be performed

Briefly, at visit 1:

- Subjects will arrive fasted for at least 12 h prior to this visit (water ok).
- A finger stick blood sample will be collected (to confirm fasting).
- Concomitant medications and accomplishment of inclusion and exclusion criteria will be reviewed.
- 24-hs food and physical activity questionnaire
- Seated resting blood will be measured.
- Weight will be measured.
- Venous blood samples will be collected for analytical determinations (20 ml).
- A hematocrit will be performed in order to discard anemia.
- Snack ingestion
- Hand grip strength and SPPB test will be completed.

- The supplement will be provided to the subjects for a 3 weeks supplementation period.
- Stool and urine collection kit and a standardized log and instructions (**Attachment G and H**) will be provided to subjects. The kits will be returned at visit 2.

Visit 2 (3-weeks visit):

Subjects will return to the Ragle Facility for the follow-up visit. This visit will take approximately 2 h to complete.

Briefly, at visit 2:

- Subjects will arrive fasted for at least 12 h prior to this visit (water ok).
- Subjects will provide fecal and urine samples collected with the collection kit.
- A finger stick blood sample will be collected (~1 drop).
- Concomitant medications and accomplishing of inclusion and exclusion criteria will be reviewed.
- 24-hs food and physical activity questionnaire
- Seated resting blood pressure will be measured.
- Weight will be measured.
- Subjects will take the assigned supplement.
- Venous blood samples will be collected (20 ml).
- A hematocrit will be performed in order to discard anemia.
- Snack will be provided to the participants.
- Hand grip strength and SPPB test will be completed.
- Enough supplement will be provided to the subjects for a 3 weeks supplementation period.
- Unused and empty packages of the study product will be return.
- Stool and urine collection kit will be provided to subjects. The kits will be returned at visit 3.

Visit 3 (final visit):

Subjects will return to the Ragle Facility for the final visit. This visit will also take approximately 2 h to complete.

Briefly, at visit 3:

- Subjects will arrive fasted for at least 12 h prior to this visit (water ok).
- Subjects will provide fecal and urine samples collected with the collection kit.
- A finger stick blood sample will be collected (~1 drop).
- Concomitant medications and accomplishing of inclusion and exclusion criteria will be reviewed.
- 24-hs food and physical activity questionnaire
- Seated resting blood pressure will be measured.
- Weight will be measured.
- Subjects will take the assigned supplement.
- Venous blood samples will be collected (20 ml).
- A hematocrit will be performed in order to discard anemia.
- Snack will be provided to the participants.
- Hand grip strength and SPPB test will be completed.
- Unused and empty packages of the study product will be return.

10) Study Timelines

Duration of individual subject's participation will be ~6 weeks. The study will include: 1 visit (visit 0) for the screening process that will last approximately 2 h and 3 more visits (visits 1, 2 and 3) for intervention process that will last approximately 2 h each. Visit 0 will involve an in-person screening to obtain written informed consent and determine if subjects meet the inclusion/exclusion criteria. Visit 1, 2 and 3 (at 0, 3 weeks and at the end of the 6 weeks, respectively) will include blood sample collection and tests performance.

11) Study Endpoints

Primary endpoint:

Hand-grip strength media value of 16 kg or lower

Secondary endpoints:

Levels of Irisin as a marker of sarcopenia

Glucose, Insulin, GLP-1, GLP-2, GIP, Adiponectin, leptin and ghrelin, Blood urea nitrogen, creatinine, Aspartate transaminase, Alanine transaminase, Total cholesterol, triglyceride, high-density lipoprotein (HDL), low-density lipoprotein, IL-6, IL-15, 25-hydroxyvitamin D as markers of general metabolism state.

12) Data and/or Specimen Management and Confidentiality

Data management: The de-identified data will be analyzed for statistical significance with the help of the Biostatistics group at UC Davis, including univariate graphical, analytic summaries and bivariate relationships using box plots, scatter plots, and correlations. To compare participants in the two diet groups (Placebo control and freeze-dried table grape powder) a paired Student's t test (two-tailed) will be used. Data involving more than two repeated measures, such as grip strength tasks, or irisin levels, will be assessed by repeated measures (ANOVA). Differences will be considered significant at $P < 0.05$. Significant results will be also subjected to analysis of covariance (ANCOVA) to account for group differences at baseline and post hoc comparisons using the Bonferroni correction.

Data confidentiality: After obtaining written informed consent, all subjects will be assigned an identification number (ID) and all data and specimens will be collected from individuals and stored using this ID number. The key linking the subjects' personal information to their laboratory results will be kept in a locked drawer in the investigator's office. Only authorized research personnel will have access to the study data. People outside the research process will not have access to results about any one person. Staff analyzing the data will only have access samples identified by subjects' ID number. The subjects'

personal information (questionnaires and consent form) will be kept separately under lock and key in the investigator's office

13) Withdrawal of Subjects

Possible reasons for removal include specific muscle diseases, peripheral vascular disease, intermittent claudication, central and peripheral nervous system disorders, cachexia, active diagnosis of diabetes mellitus, myocardial infarction, stroke, liver disease, on dialysis or long-term steroid therapy, and/or actively receiving treatment for cancer or severe infection (excluding short-term antibiotic therapy) that are diagnosed ones the subject are already enrolled in the study. If the participants start taking supplements. Also, if the participants experiment a remarkable increment in body weight, blood pressure and plasma glucose and cholesterol concentrations above 100 and 200 mg/dl. Finally, development of anemia during the study will be another reason for removal.

14) Risks to Subjects

Venipuncture: Risks of venipuncture include some discomfort, bruising, and rarely, infection. Blood collections will be performed by a registered nurse to minimize discomfort.

Blood volume: The amount of blood to be drawn during the study will be ~60 mL, collected over a period of 6-weeks. We will take a finger stick blood sample (~1 drop, equal to ~100 ul) at visits 0, 1, 2 and 3 and 20 mL/visit at visits 1, 2 and 3. These volumes are well within the recommended allocated volume for healthy adults. Nevertheless, the patients could experiment dizziness, nausea and physical weakness.

Study products: The components of the dietary supplement and placebo are detailed in **Attachment I** and **Attachment J**, respectively. The dose that the participant will consume daily is the equivalent to a ~150 g (1.5 cups) of fresh grapes, which won't represent a health risk for the participant

15) Potential Benefits to Subjects

No direct benefits to the individual subjects are anticipated. However, subjects will receive general information regarding their overall health status.

16) Provisions to Protect the Privacy Interests of Subjects

Subjects will be assigned an identification number (ID) and all data and specimens will be collected and stored using this ID number. Personal information (name, phone number and email address) and consent forms will be kept in confidence and will be stored in a locked cabinet in the investigator's office. The key linking the subjects' personal information to their laboratory results will be kept separately in another locked drawer in the investigator's office (See above for more on confidentiality).

At the Ragle Facility, the subjects will interact with the study coordinator and trained research personnel. The data collection (anthropometry, blood pressure and venipuncture) will be performed in individual secluded rooms by trained research personnel. We will ensure that the subjects feel comfortable with all research procedures. Questions and interactions between the subjects and the research team will be kept private.

17) Sharing of Results with Subjects

Subjects will receive the results of their blood screen (once reviewed and approved) at the time of completion of the study (or early withdrawal). The research data will not be shared with the subjects, but a summary of the research can be provided to the subjects who express interest.

18) Data/Specimen Banking

All samples, including those sent out for outside analysis will have only a numerical identifier and date/time. Specimens to be stored on site will be kept frozen at -80°C in secure laboratories. Specimens will be stored as long as they are viable for analyses; records of storage will be kept by the investigator's lab staff; all records will be of the de-identified specimens. During analyses, the de-identified data will be entered in Excel

files and analyzed for statistical significance using SAS in password protected computers.

19) Multi-Site Research

This is a single site study.

20) Community-Based Participatory Research

N/A

21) Review Requirements

Some research projects require specific IRB determinations.

1. Are there any contractual obligations or other considerations that require IRB review of this research, or review at intervals other than those required by the Common Rule or FDA?

Yes

No

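### Section 4 sizes the trial on irisin as the primary outcome, but Section 11 makes irisin secondary and gives as primary a grip threshold copied from the inclusion criteria

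*Protocol*

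**What the plan says.** Section 4 (Enrollment Numbers) takes change in plasma irisin "as our primary outcome to determine the power calculations for sample size". It requires 5 per group for 80% power at a two-sided alpha of 0.05 and enrols 7 per group, 14 in all, to allow for dropout. No other sample-size calculation is given.

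Section 11 (Study Endpoints) has one primary endpoint: "Hand-grip strength media value of 16 kg or lower". Its secondary list begins with "Levels of Irisin as a marker of sarcopenia".

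Section 5 (Inclusion and Exclusion Criteria) admits "postmenopausal women aged 60 years or older with a hand-grip strength media value of 16 kg or lower". The Section 11 primary endpoint is the last part of that criterion, word for word.

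Section 12 (Data management) plans to compare the two diet groups. It says that outcomes with more than two repeated measures, "such as grip strength tasks, or irisin levels, will be assessed by repeated measures (ANOVA"), and it does not rank the two outcomes.

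Section 2 (Objectives) has one aim on sarcopenia parameters and a second on "key metabolic regulators of sarcopenia in postmenopausal women, specially irisin". It also says that "The successful completion of this pilot human study" is to supply preliminary results for a larger grant application.

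**The concern.** Irisin cannot be both the primary outcome and a secondary endpoint. The endpoint that Section 11 does call primary cannot be analysed as written. It describes a state that all participants are in at entry, and it does not say whether being in that state at the end is a good or a bad result.

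Two things follow. First, the outcome reported as primary could be picked after the results are known, with a false-positive risk above the nominal 5%. Second, if grip is the primary endpoint, the trial's only power statement concerns a different variable. A null grip result from 14 women could then be read as evidence of no effect from a trial said to have 80% power. Because this is a pilot, the harm is mainly an unclear headline rather than a failed confirmatory test, but that headline is meant to support the next application.

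**Working it through.** **1. The statements side by side**

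| Place | Irisin | Grip strength |
|---|---|---|
| Section 2 | second aim | covered by first aim (sarcopenia parameters) |
| Section 4 | primary; sizes the trial | not mentioned |
| Section 5 | not mentioned | entry criterion, 16 kg or lower |
| Section 11 | secondary | primary, same 16 kg wording |
| Section 12 | repeated-measures ANOVA | repeated-measures ANOVA |

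Nothing in the table breaks the tie between Sections 4 and 11.

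**2. The protocol's own sample size**

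Section 4 gives no effect size or SD, so 5 per group cannot be reproduced forwards. Solving backwards for 80% power at two-sided 0.05 with the exact noncentral t:

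- Paired t-test, the test Section 4 names: n = 5, df = 4, noncentrality dz × √5, giving dz = 1.68.
- Independent groups: n = 5 per arm, df = 8, noncentrality d × √(5/2), giving d = 2.02.

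The step from 5 to 7 equals 5 / (1 − 2/7) = 7, so it allows for losing 2 of 7 per group. All of this concerns irisin only.

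**3. Power if grip is primary**

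Take change in grip, grape versus placebo, two-sample t-test, two-sided 0.05. For n per arm, df = 2n − 2 and the noncentrality is d × √(n/2), where d is the difference in SD units.

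| n per arm | d | Noncentrality | Power |
|---|---|---|---|
| 7 | 1.63 | 1.63 × √3.5 = 3.05 | 80% |
| 5 | 2.02 | 2.02 × √2.5 = 3.19 | 80% |
| 7 | 1.0 | 1.0 × √3.5 = 1.87 | 41% |
| 7 | 0.8 | 0.8 × √3.5 = 1.50 | 28% |

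The protocol gives no SD for change in grip. Assuming 1.5 to 3 kg, 1.63 SD is 1.63 × 1.5 = 2.4 kg to 1.63 × 3 = 4.9 kg, in women who enter at 16 kg or lower.

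**4. Power if the 16 kg threshold is taken literally**

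Suppose the endpoint were the proportion still at or below 16 kg at the end. The rates here are assumed. With 90% on placebo versus 50% on grape, Fisher's exact test has about 13% power at 7 per arm. With 100% versus 50% it has about 23%. For 80% power, a normal-approximation calculation needs 20 and 11 per arm respectively.

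**5. False-positive risk if either outcome may be called primary**

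For two independent null outcomes each tested at 0.05: 1 − 0.95² = 0.0975. For correlated outcomes, from 200,000 simulated null trials with 7 per arm and a two-sample t-test on each outcome:

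| Correlation | Chance that at least one is significant |
|---|---|
| 0.3 | 9.6% |
| 0.5 | 9.2% |
| 0.7 | 8.6% |
| 0.9 | 7.2% |

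**The case against.** The best defence is that Section 4 only names the variable chosen for powering, while the section that defines endpoints names just one primary, grip. The background supports this: Section 2 puts sarcopenia parameters first, and Section 3 cites a consensus that treats low muscle strength as the main parameter for assessing sarcopenia. This makes grip the more likely intention, but it does not remove the conflict, because Section 4 still calls irisin the primary outcome. On this reading the true primary endpoint has no sample-size basis at all.

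Second, Section 12 does state a comparison of the two diet groups, with ANCOVA for baseline differences in significant results, and finer detail may sit in a statistical analysis plan that is not at hand. A contrast is indeed stated, but it serves grip and irisin equally and does not identify the primary. An analysis plan would inherit the conflict rather than resolve it.

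Third, a threshold repeated from entry could still be compared between groups as the proportion who remain below it. That is true, but Section 11 does not say so, Section 12 plans a continuous analysis, and the threshold form has little power at this size.

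Fourth, the 9.75% is an upper bound that assumes free choice between two outcomes, and the kilogram range rests on an assumed SD. Both points stand. The contradiction depends on neither figure.

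**Conclusion.** The concern holds. The protocol contradicts itself on its primary outcome, and the endpoint listed as primary in Section 11 is an entry criterion rather than a treatment effect. This rests on the text alone and is certain.

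The size of the consequence depends on the reading. If the choice is left open, the risk of a false primary claim is roughly 7% to 10% instead of 5%, assuming one test per outcome. If grip is primary, the stated 80% power does not carry over; assuming a continuous change and a two-sample t-test, only a difference of about 1.6 SD would be detected with 80% power if all 14 women complete, and about 2.0 SD if 5 per arm remain.

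A smaller point is probable rather than certain. *Media value* in Sections 5 and 11 is undefined and probably means the mean, whereas Section 8 says "The best of the 3 grip strength measurements will be used in statistical analyses". Three readings are taken per side, and no hand is specified. Attachment D, not at hand, may settle this.

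**What to change.** Name one primary endpoint in identical words in Sections 4, 11 and 12: a continuous change from visit 1 to one stated visit (for example visit 3, at 6 weeks), grape versus placebo.

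- **If irisin is primary**, move grip to the secondary list in Section 11.
- **If grip is primary**, call irisin secondary in Section 4. State there that the 80% power does not apply to grip and give the detectable difference at 7 per arm, or provide a new sample-size basis.

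In either case, keep the 16 kg cut-off as an eligibility rule only. Define *media value*, and state one grip summary (which hand or hands, mean or best reading) for use at every visit.

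The cost on this point is wording only if irisin stays primary. That does not endorse the 80% figure for irisin, which is a separate matter: Section 4 gives no effect size or SD and names a paired test for two randomised groups. Choosing grip costs more, because the trial then needs either a larger sample or a plain statement that its primary endpoint is not powered. The change should be made before any outcome data are seen.
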